2.10. Rationale for outcome measurements

Our outcome measures are all well validated clinical outcomes for use in studies of asthma, and validated questionnaires for assessing likely side effects. We are including a number of feasibility outcomes that will inform the decision to proceed with a definitive multi-center clinical trial: these include assessment of recruitment and retention, adherence and non-compliance (from pill counts, diary cards, missed visits) and side-effects (from GSRS, PHQ-9 and GAD-7). Participants with scores on the PHQ-9 or GAD-7 that reach the thresholds for exclusion outlined in the eligibility criteria will be discontinued from study drug, the site specific plan for caring for these participants will be instituted, and they will be followed for the rest of the study off of study drug.

Baseline medical and asthma control questionnaires will take 20-30 minutes to complete, will be completed at the Medical Office Building, in a private office. Questionnaires are in paper format, and will be completed by the participant.

2.11. Modifications due to COVID-19 pandemic

Due to the COVID-19 public health emergency, TRIM, will permit remote follow up of enrolled participants as of April, 6, 2020. Participants enrolled after re-opening of the study should be seen at in-person visit for V2 (randomization visit) and V7 (24 weeks), other visits can be conducted in-part or fully remotely. It is possible that research activities will face restrictions in the future or that a participant will prefer to do the V4-V6 remotely, so we will provide participants with a scale and tape measure to collect data for remote visits. All questionnaires can be conducted remotely prior to in-person visits for all visits. Participants who are followed up remotely, will complete some questionnaires over the phone and mail back the rest of the questionnaires to the site. Methacholine challenge tests and spirometry should not be conducted. Women of child-bearing potential and participating in remote follow up will be mailed testing kit, and asked to send photo of result to coordinator

3. Data analysis

The appropriateness of the human, technological and systems components of the data acquisition and management procedures will be analyzed including practicality of data acquisition, estimation of likely participant characteristic and outcome distributions, suitability and functionality of paper and electronic forms, and resources required for participants contact and follow up, and to anticipate rates for missing data.

3.1. Primary analysis

The primary statistical analysis will be an unadjusted comparison of 24-wk change in ACT between treatment groups. A linear mixed effects model will be used to model the change in ACT over time. A saturated means model, including indicators for each time point, treatment and treatment by time interaction, will be specified and a random effect for individual will be used to account for the repeated measurements over time. The 24-week treatment by time interaction term represents the difference in change in ACT between the treatment groups, i.e. the primary outcome. If the data are non-normal, then transformations and non-parametric alternatives (e.g. Wilcoxon Rank-Sum test comparing the raw differences from baseline to 24-weeks between treatment groups) will be explored. If imbalances in influential baseline variables are present, then secondary analyses using appropriate stratification or adjustments will be done. Sensitivity analyses using alternate mean and covariance structures will also be performed. Analyses will be done based upon principles of intention to treat, i.e. all data from all randomized participants will be included in the analysis.

Secondary analyses will focus on the effects of additional covariates including age, gender, site, BMI >40, baseline ACT score, and adherence with treatment. These models will build on primary analysis described above. Potentials risk factors will be added as a main effect to reduce variability and interaction effect to identify potential subgroup effects. Analyses using adherence measures will be performed to explore dose-response relationships.

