2.1. Eligibility criteria

2.1.1. Inclusion criteria

- Physician diagnosis of asthma and on regular prescribed controller therapy for at least 3 months
- Previous (within five years) evidence of at least a 12% increase in FEV₁ after inhaling 2-4 puffs of albuterol or a positive methacholine challenge or patient reported history of improvement of asthma exacerbation after a course of systemic or inhaled corticosteroids.
- Age: ≥18 years of age
- Obese: BMI > 30 kg/m²
- Poorly controlled asthma: Asthma Control Test Score < 20, or use of rescue inhaler, on an average of > 2 uses/week for preceding month, or nocturnal asthma awakening, on an average of 1 or more times / week in preceding month, or ED/hospital visit or prednisone course for asthma in past six months.
- Ability and willingness to provide informed consent

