3.2. Secondary outcomes

Secondary outcomes include ASUI, mAQLQ, and GSRS scores, lung function, weight loss and adverse events. Continuous outcomes, scores and lung function, will be analyzed similarly to the primary outcome. Event outcomes will be analyzed in two ways: negative binomial regression to estimate rates and Kaplan-Meier curves and Cox proportional hazard models for time-to-first event.

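### A cheap improvement, not an error: the primary week-24 ACT contrast leaves baseline means free by arm and usually gives up precision that conditioning on baseline ACT would recover

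*Combined protocol and SAP*

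**What the plan says.** Section 3.1 makes the raw change comparison primary: "The primary statistical analysis will be an unadjusted comparison of 24-wk change in ACT between treatment groups". On the model it says: "A saturated means model, including indicators for each time point, treatment and treatment by time interaction, will be specified", with a random effect for individual. The 24-week interaction is the primary result.

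Baseline ACT enters only later: "Secondary analyses will focus on the effects of additional covariates including age, gender, site, BMI >40, baseline ACT score, and adherence with treatment". These models build on the primary one, and covariates enter as follows: "Potentials risk factors will be added as a main effect to reduce variability and interaction effect to identify potential subgroup effects". Adjustment for baseline imbalance is also secondary. The section adds: "Sensitivity analyses using alternate mean and covariance structures will also be performed". It names no particular structure.

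Section 3.2 carries the approach over to ASUI, mAQLQ and GSRS: "Continuous outcomes, scores and lung function, will be analyzed similarly to the primary outcome".

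Section 3.3 sizes the pilot on a one-sided 90% limit for the difference in ACT change, with 28 to 34 participants before inflation to 38. The visit table in Section 2.9 collects ACT at both V1 (week -1) and V2 (week 0). Section 3.1 does not say which is baseline.

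**The concern.** Randomization makes the arms' baseline means equal in expectation. A model with a treatment main effect at baseline ignores this and carries all the chance difference at baseline into the change contrast. Conditioning on baseline removes the part that week-24 ACT does not share.

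Section 3.3 says the ACT limit could inform the decision on a definitive trial, and Section 2.10 lists feasibility outcomes as further inputs. In a trial of 38, a narrower limit that costs no patients or visits is worth having.

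The plan also appears to want this precision, since it gives reducing variability as the reason for adding covariates. Under the likelier reading of the model, the step it describes cannot achieve that for the week-24 contrast.

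**Working it through.** **Inputs.** From Section 3.3: SD 5, read as the SD of change because it accompanies a difference in changes; target difference 2.8; 28 to 34 completers; one-sided 90% limit. From Section 2.6: equal allocation. Assumed, because the documents do not give them: baseline-to-week-24 correlation r = 0.3 to 0.8, and k = baseline SD / week-24 SD = 0.7 to 1.0. Values of k below 1 are plausible because a low ACT is one entry route (Section 2.1.1: "Poorly controlled asthma: Asthma Control Test Score < 20, or use of rescue inhaler").

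**Step 1: the plan's own figures.** The standardized limit is 1.2816 × 2/√N. N = 28 gives 0.4844 and N = 34 gives 0.4396 (the table has 0.4397, a rounding difference). In ACT points at N = 34, SE = 5 × 2/√34 = 1.715 and the limit is 1.2816 × 1.715 = 2.20. At N = 28, SE = 1.890 and the limit is 2.42. Both limits are below 2.8.

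**Step 2: what the planned model estimates.** It was fitted to one simulated complete data set (38 participants, six visits, equal SDs, r = 0.5):

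| Model | Week-24 contrast | SE |
|---|---|---|
| As planned | -1.1945 | 1.878 |
| Planned plus baseline ACT main effect | -1.1945 | 1.878 |
| Common baseline mean | -0.5094 | 1.578 |
| Post-baseline visits, baseline as covariate | -0.3972 | 1.610 |

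The raw difference in mean change was also -1.1945. Three further data sets with 34 participants again gave the same estimate and SE, to four decimals, with and without the baseline main effect.

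This depends on baseline being part of the response. If the response is post-baseline change, the main effect does help: in three simulated data sets the SE fell from 1.584 to 1.324, from 1.630 to 1.379, and from 1.75 to 1.52.

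**Step 3: size of the gain.** Variance ratio, conditioned to change = (1 − r²)/(1 + k² − 2rk) × (N − 3)/(N − 4). The last factor is the cost of estimating the slope. For example, r = 0.3, k = 1, N = 34 gives 0.91/1.40 × 31/30 = 0.672. The SE is then 1.715 × √0.672 = 1.406, a fall of 18.0%, and the limit is 1.80.

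SE change and null-result limit at 34 completers:

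| k | r = 0.3 | r = 0.5 | r = 0.7 | r = 0.8 |
|---|---|---|---|---|
| 1.0 | -18.0%, 1.80 | -12.0%, 1.93 | -6.3%, 2.06 | -3.6%, 2.12 |
| 0.9 | -14.0%, 1.89 | -7.7%, 2.03 | -2.1%, 2.15 | +0.3%, 2.20 |
| 0.8 | -10.0%, 1.98 | -3.9%, 2.11 | +0.7%, 2.21 | +1.7%, 2.23 |
| 0.7 | -6.3%, 2.06 | -1.0%, 2.18 | +1.7%, 2.23 | +0.3%, 2.20 |

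The loss is largest when r = k. The regression slope is then 1, conditioning equals the change score, and only the slope cost remains: √(31/30) = 1.017. At 28 completers the SE change runs from -17.7% to +2.1% and the limit from 1.99 to 2.47.

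**Step 4: chance of excluding 2.8 when there is truly no effect.** Φ(2.8/SE − 1.2816) is 64% unadjusted at N = 34, and 63% to 76% over the grid. This is an operating characteristic computed here; the plan does not promise it.

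**The case against.** **The plan is sound on its own terms.** The contrast is unbiased, matches how Section 3.3 sizes the trial, and meets a criterion that is conditional on seeing no effect. This stands. A reader might infer that the primary analysis is wrong or the pilot underpowered. The documents do not support that, and the 64% figure is no evidence of a broken commitment.

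**The gain is unknown and may be nil.** This also stands. For k of 0.7 to 0.8 and r of 0.5 or more, the SE falls by at most 3.9% and may rise slightly. Large gains need a low correlation or similar SDs at the two visits.

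**The plan already covers it.** This stands only in part. A common-baseline model would fit under alternate mean structures, but none is named and a sensitivity analysis leaves the primary estimate as it is. The baseline main effect helps only if the response is post-baseline change. Section 3.1 does speak of modelling change over time, so that reading is open. However, the saturated time terms and the identification of the 24-week interaction with the difference in change favour baseline being in the response.

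**Unbiased does not mean fully valid.** A reader might also take this point as clearing the planned model entirely. It does not. A random effect for individual alone implies compound symmetry, and its SE is right only then. One simulation let the correlation with baseline fall from 0.7 at week 2 to 0.3 at week 24, extended by lag as an assumption, with 17 per arm. The model's mean SE was 1.41 against a true value of about 1.70, and a nominal 5% test rejected about 11% of the time. That is a separate issue, partly met by the planned alternate covariance structures.

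**Conclusion.** The point holds as a recommended efficiency improvement and not as a finding of error. The primary contrast is unbiased but usually less precise than one that conditions on baseline ACT. Under the assumed ranges and 34 completers, the effect on the SE lies between an 18% fall and a rise of about 2%, so the possible gain is much larger than the possible loss. The direction is well supported. The size is not known, because it rests on a correlation and an SD ratio that the documents do not give. It also rests on reading SD 5 as the SD of change. If 5 is a per-visit SD and the SDs are equal, the SD of change is 5.92, 5.00 or 3.87 at r = 0.3, 0.5 or 0.7, against 4.77, 4.33 or 3.57 after conditioning, which is the same direction.

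**What to change.** Make the primary model a repeated-measures model with every visit from V2 onward in the response, one common baseline mean for both arms, an unstructured covariance and a small-sample degrees-of-freedom correction. The week-24 contrast stays primary. The unstructured covariance also removes the reliance on compound symmetry.

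Pre-specify a fallback for non-convergence, since six visits mean 6 × 7/2 = 21 covariance parameters in a sample of 38. One option is post-baseline ACT with baseline and baseline-by-visit terms. Note in the SAP that it drops participants with no post-baseline ACT. By-visit slopes are preferable to one pooled slope, but the difference is small: in a simulation with falling correlation the SE fell 18.0% against 16.9% at k = 1, and 6.1% against 4.8% at k = 0.7.

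Do not make a week-24-only ANCOVA primary. It discards the interim visits of anyone missing V7, which conflicts with the intention-to-treat commitment in Section 3.1 to use everyone's data.

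Keep the unadjusted change comparison as a sensitivity analysis. Do not add baseline ACT as a covariate to any model that also has baseline in the response. State that V2 is the ACT baseline: it is the natural reading, since only V2 to V7 spans 24 weeks, but the plan does not say so. Apply the same choices to the continuous secondary scores.

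The cost is SAP wording and a modest change to code, with no new data, visits or patients. The statistical downsides are a possible SE rise of about 2% and more covariance parameters to estimate in a small sample.

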- Medical Outcomes Study (SF36) is a measure of general health related quality of life which correlates with asthma outcomes.^{23,24}

- The Patient Health Questionnaire for Depression and Anxiety (PHQ9 and GAD7) will be used. The Patient Health Questionnaire is a diagnostic tool for mental health disorders used by health care professionals that is quick and easy for patients to complete. We have used this questionnaire in prior ALA-ACRC studies, and so the centers are familiar with its use. We will use sections specific to mood (PHQ-9) and anxiety (GAD-7). The PHQ-9, a tool specific to depression, scores each of the 9 DSM-IV criteria based on the mood module from the original PRIME-MD. The GAD-7 was subsequently developed as a brief scale for anxiety and scores seven common anxiety symptoms.^{25,26}
- Anthropometrics will include blood pressure, height and weight, and waist and hip circumference per NHANES III.²⁷ Digital scales will be given to participants at visit 2 to take home to measure weight. Participants will be asked to send a photo of the weight shown on the scale along with their feet to the coordinator.
- Adverse effects will be assessed by open-ended questions at each visit and rated in severity.
- Interval health history will be recorded at each clinic visit. Records of all hospitalizations and, if necessary, deaths are obtained for verification of diagnoses and assessment of safety issues.
- Baseline questionnaires and exam will be administered to ascertain demographics including self-reported ethnicity and race, general health, co-morbid conditions, asthma symptoms, and medication use.
- Assessment of Adherence: adherence will be assessed from pill counts when participant returns pills at each study visit after randomization. If only remote visits are permitted, then pill count will be completed when participant mails back drug bottles at the end of the study.
- Exit questionnaires will be administered at the last visit to determine global assessments of treatment, adequacy of informed consent procedures, satisfaction with study procedures and personnel, and opinions about the intervention.
- Blood specimens will be collected for fasting blood glucose and analysis of metabolic and oxidative markers related to asthma if a site permits this. Excess blood specimens will be used for future asthma research with the patient's consent. Fasting blood draw may take place within 7 days of rest of the procedures scheduled for visit 2 or visit 7.

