4.2.1. Protocol for participant with elevated depression and anxiety symptoms

The PHQ-9/ GAD-7 captures the presence and severity of depression and anxiety symptoms. Scores above the specified thresholds suggest a clinically significant level of psychological distress. It does not necessarily mean that the participant has a clinical diagnosis of depression or anxiety but may indicate the need for appropriate care. **Study personnel will be instructed to tabulate and review the scores for these instruments before the participant is released from the study visit.**

Participants with scores on the PHQ-9 or GAD-7 (including those being screened for the eligibility who do not qualify for the study) that reach or exceed the thresholds for exclusion outlined in the study eligibility criteria will be discontinued from study drug under the supervision of the site PI (if on study drug), and the site PI will ensure that the site specific plan for managing these participants is instituted. Participants already randomized into the study will continue to be followed for the rest of the study off of study drug (unless they decide to withdraw). Subsequent scores exceeding the threshold score, or the minimally clinically important difference for the questionnaires when compared to Visit 2 (≥ 5) will be considered an adverse event, and, as such, followed until resolution or a plan for care under the supervision of another medical provider is established. This will be considered an adverse event, and, as such, followed until resolution or a plan for care under the supervision of another medical provider is established. Participants will be informed that the elevated score could be related to the study drug, though investigators and subjects will not be unblinded to treatment assignment.

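### Adherence is measured after randomization but listed with baseline covariates and used for dose-response; some permitted models would bias the treatment contrast, and the dose-response slope is confounded

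*Combined protocol and SAP*

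**What the plan says.** Section 3.1 sets an unadjusted intention-to-treat primary analysis: a random-intercept mixed model with visit indicators, treatment and treatment-by-time, read at week 24. It then adds secondary models:

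- The factors are named in one list: "Secondary analyses will focus on the effects of additional covariates including age, gender, site, BMI >40, baseline ACT score, and adherence with treatment".
- The model form is described only by reference back to the main model: "These models will build on primary analysis described above".
- On how a factor is to enter, the plan has this: "Potentials risk factors will be added as a main effect to reduce variability and interaction effect to identify potential subgroup effects".
- Adherence then has a second, separate use: "Analyses using adherence measures will be performed to explore dose-response relationships".

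Section 2.9 gives the source of the measure: "adherence will be assessed from pill counts when participant returns pills at each study visit after randomization". If only remote visits are permitted, there is a single count when the bottles are mailed back at the end.

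Two features of the protocol let assignment or health state alter intake. Under section 2.10, participants whose PHQ-9 or GAD-7 scores reach the thresholds "outlined in the eligibility criteria will be discontinued from study drug", and section 4.2.1 adds: "Participants already randomized into the study will continue to be followed for the rest of the study off of study drug". Section 4.1.1 expects more gastrointestinal and psychiatric events on roflumilast than on placebo, including an excess of 11.1% for nausea and 9.7% for diarrhea over 24 weeks.

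**The concern.** Of the six listed factors, adherence is the only one not fixed at randomization. Two separate problems follow.

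1. **Treatment contrast.** If roflumilast lowers adherence through side effects or the stopping rule, and adherence is also related to ACT change for other reasons, then conditioning on adherence no longer compares randomized groups. Whether this moves the 24-week contrast depends on how adherence enters the model, and section 3.1 does not say.
2. **Dose-response.** Who takes the tablets is not randomized. People who are well, motivated or tolerant may both take more and improve more. A within-arm slope of ACT change on adherence mixes this with any drug effect, even when adherence is the same in both arms.

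At stake are the secondary results only: an artefact could be reported as an adherence subgroup effect or a dose-response.

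**Working it through.** The plan gives no figure for this point to reproduce, and no adherence rate. What follows is an illustration with zero drug effect, not a prediction.

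**Inputs from the documents.** SD of ACT change 5 (section 3.3); 38 participants, 19 on roflumilast, 1:1 (sections 2.8, 3.3, 4.1.1); excess psychiatric events 7.1 and nausea 24.0 per 100 patient-years (section 4.1.1); visits at weeks 0, 2, 6, 12, 18 and 24.

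**Assumptions.**
- A share p of each arm (10, 15 or 20%) is non-adherent, with ACT change d points worse (2, 3, 4 or 5).
- A further share q of the active arm is non-adherent from side effects only, with no difference in outcome.
- Anchors for q, as if every excess case led to missed doses: 7.1 × 24/52 = 3.3% (0.6 of 19 people) and 24.0 × 24/52 = 11.1% (2.1 of 19). The second matches the protocol's nausea figure. q = 20% is a sensitivity value with no source in the documents.

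**Formulas.** Both arms have mean change −pd, so the true and unadjusted differences are 0. The adherer-minus-non-adherer slope is d on placebo and d·p/(p+q) on active. The adjusted difference is the pooled within-arm slope times q, where the pooling weights are p(1−p) and (p+q)(1−p−q).

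**Worked case, p = 0.10, q = 0.111, d = 3.**
- Slopes: 3.00 on placebo; 3 × 0.10/0.211 = 1.42 on active.
- Weights: 0.0900 and 0.211 × 0.789 = 0.1665.
- Pooled slope: (3.00 × 0.0900 + 1.42 × 0.1665)/0.2565 = 1.98.
- Adjusted difference: 1.98 × 0.111 = +0.22 in favour of roflumilast.
- Contrast within non-adherers: 3.00 − 1.42 = +1.58; within adherers: 0.

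**By model form.** These are expected values of the week-24 treatment-by-time term from generalized least squares. They assume a linear decline, random-intercept SD 3, and residual SD 5/√2 so that the SD of change is 5. Visit-level adherence falls after week 2.

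| Form of the adherence term | q = 0 | q = 3.3% | q = 11.1% | q = 20% |
|---|---|---|---|---|
| Time-constant main effect | 0.00 | 0.00 | 0.00 | 0.00 |
| Treatment × adherence, no time | 0.00 | 0.00 | 0.00 | 0.00 |
| Visit-level adherence | 0.00 | 0.03 to 0.09 | 0.09 to 0.27 | 0.13 to 0.42 |
| Adherence × time, or change-score adjustment | 0.00 | 0.06 to 0.15 | 0.15 to 0.44 | 0.21 to 0.70 |

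The time-constant forms do no harm with complete data because the contrast is then estimated within participants. With treatment × adherence × time and q above 0, the contrast is 0 in adherers and d·q/(p+q) = +0.3 to +3.3 in non-adherers. Its standard error is 5√(1/(19p) + 1/(19(p+q))) = 3.1 to 4.8.

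**Scale.** The standard error of the arm difference is 5√(4/38) = 1.62. The largest bias in the last row is 0.44/1.62 = 27% of it at q = 11.1%, and 0.70/1.62 = 43% at q = 20%.

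**Dose-response.** With q = 0 the treatment contrast is 0 in every form, yet the false slope is d, that is 2 to 5 points, in both arms. With q from 3.3 to 20% it is 0.7 to 4.3 on active and 2 to 5 on placebo.

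**Second check, different model.** A large simulation used continuous adherence (placebo mean about 0.79), a shared health factor worth 1 or 2 ACT points per SD, and a drug that lowers adherence by 10 or 20 percentage points but has no effect on ACT.
- A time-constant main effect left the contrast unchanged.
- Adherence × time gave +0.40 to +1.76; visit-level adherence gave +0.24 to +1.09.
- With no drop in adherence the adjusted contrast stayed near 0, but the active-arm slope was still +0.5 to +1.0 points per 10 percentage points of adherence. Across all settings the placebo slope was almost the same as the active slope.
- With 38 participants and the strongest settings, nominal 5% tests rejected 18% of the time for treatment given adherence and 34% for the active-arm slope.

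**The case against.** The strongest reply is that little depends on these analyses. They are secondary, in a 38-person pilot, and the dose-response is only to be explored. Sections 2.10 and 3.3 tie the next trial to feasibility outcomes and the pilot confidence limit. That stands, and it keeps the point away from the primary analysis, but a planned analysis that can yield a dose-response for an inert drug still merits correction.

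Next, the simplest reading is harmless: a time-constant main effect gives no bias. True, but a subgroup effect on change over time would naturally be fitted as an interaction that includes time, and the text does not exclude one.

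Third, the sentence on main effects and interactions speaks of risk factors, and adherence then has its own sentence, so adherence may not be meant for adjustment. This is possible. However, adherence is in the list immediately before and nothing takes it out, and the dose-response problem remains on either reading.

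Fourth, visit-level adherence cannot be fitted for anyone with only one end-of-study count. This is correct, and it limits one form among several.

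Last, the sizes are assumed. A 5-point deficit is a full SD, and the 43% figure needs q = 20%. This is also correct: with q no higher than the document-based anchors, the grid's bias is at most 0.44 points.

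**Conclusion.** The concern holds and should be corrected. Section 3.1 treats a post-randomization measure as if it were a baseline covariate, and commits to a dose-response analysis without a safeguard.

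Bias in the 24-week contrast needs two things: assignment must affect adherence, and the model must use adherence-by-time, visit-level adherence, change-score adjustment or adherence subgroups. Confounding of the within-arm slope needs neither.

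The mechanism is established; size and direction in this trial are not. The documents give events, not missed doses, and no link between adherence and ACT. The signs reverse if non-adherers do better. The two illustrations differ in size because their assumptions differ, but agree on which forms are biased. The unadjusted intention-to-treat primary analysis is not affected.

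**What to change.** In section 3.1:

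- Limit adjustment and subgroup factors to age, gender, site, BMI >40 and baseline ACT, and delete adherence from that list.
- Report adherence by arm, as the feasibility outcome already named in section 2.10.
- Label any adherence-response analysis non-randomized and exploratory, and show the slope in both arms, with the placebo slope as a check on confounding.
- If an effect of drug actually taken is wanted, add an exploratory complier-average or instrumental-variable estimate, with assignment as instrument, active doses taken as exposure (zero on placebo) and the assumptions stated. Pill counts from both arms would not serve as the exposure: the first stage would be −q, −0.03 to −0.20, which has the wrong sign.

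The cost is wording and at most one small analysis; sample size, data collection and the primary analysis stay as they are. There are limits:

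- The placebo slope has a standard error of 5√(1/(19p) + 1/(19(1−p))) = 2.9 to 3.8 points, so a flat slope would not rule out confounding.
- If non-adherers take no drug, the instrumental-variable first stage is 1−p−q = 0.60 to 0.87. The 95% half-width is then 2.03 × 1.62 divided by that, 3.8 to 5.5 points, against 3.3 for intention to treat. It also shows no dose-response shape.

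A related point: section 2.3 describes every-other-day dosing for the first two weeks, while the visit table in section 2.9 provides for it from V3 onward. These passages must be reconciled before the pill-count denominator is set.

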1.3. Study design

A 24 week, randomized, double-masked, placebo controlled trial in 38 participants.

1 week baseline ← 24 week treatment →

V1	V2	V3	V4	V5	V6	V7
wk-1	wk0	wk2	wk6	wk12	wk18	wk24

2. Methods

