2.8. Randomization and blinding

Treatment assignments will be stratified by clinic and the allocation ratio will be (1:1). Randomization will be accomplished by keying eligibility data into the data system; after verification of eligibility, a treatment assignment number corresponding to unique study kit will be assigned. Study kits will be labeled with two-part tear-off labels with unique identifiers. The tear-off label is affixed to a study form when the kit is assigned to a participant and the information is keyed into data system to verify that assigned treatment was given to the participant.

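### The secondary covariate and interaction models name BMI only as above or below 40, which loses about one third to 45% of the information on the BMI term if its effect is roughly linear

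*Combined protocol and SAP*

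**What the plan says.** Section 3.1 makes the primary analysis an unadjusted comparison of the 24-week change in ACT. It then turns to secondary analyses of further covariates, which it lists as "age, gender, site, BMI >40, baseline ACT score" and treatment adherence. On how these enter the models it says: "Potentials risk factors will be added as a main effect to reduce variability and interaction effect to identify potential subgroup effects".

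BMI can be computed from measured data. Section 2.9 states: "Anthropometrics will include blood pressure, height and weight, and waist and hip circumference per NHANES III". The visit table in the same section schedules anthropometrics at every visit, including V1 and V2, before treatment has had any effect.

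The value 40 plays no other part in the design. Entry requires "Obese: BMI > 30 kg/m²". Section 2.6 stratifies randomization by center and age, and section 2.8 names clinic only; neither uses BMI. The size is given in section 1.3: "A 24 week, randomized, double-masked, placebo controlled trial in 38 participants".

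**The concern.** The indicator treats BMI 31 and 39 as the same, and 39.9 and 40.1 as different. Age and baseline ACT score appear in the same list without a cut point, so BMI is handled differently from its neighbours, and the plan does not say why.

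Both stated uses of the covariate suffer if BMI acts gradually. As a main effect it explains less residual variation than it could. As an interaction it gives a less precise view of whether the treatment effect changes with degree of obesity. Section 1.1 argues that part of the drug's benefit may come through weight loss, so that is a natural question for a pilot meant to prepare a definitive trial. How precisely it is answered would also depend on how many of the 38 participants happen to exceed 40.

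**Working it through.** The plan states no figure for information lost by the cut and no BMI mean, SD or share above 40, so there is nothing of its own to reproduce here. The inputs from the documents are the entry limit (BMI above 30, section 2.1.1), N = 38 with 1:1 allocation (sections 1.3 and 2.8), and an SD of 5 and target difference of 2.8 for change in ACT (section 3.3). The BMI distributions are assumptions.

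**1. Information kept on the BMI term.** With a linear BMI effect, the share kept is R², the squared correlation between BMI and the indicator for BMI above 40. R² was simulated (2 million draws per case, before truncation) for 21 distributions limited to BMI above 30. Selected cases:

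| Assumed shape (all above 30) | Mean | SD | Share above 40 | R² | Loss |
|---|---|---|---|---|---|
| Truncated normal | 39.7 | 5.7 | 44% | 0.669 | 33% |
| Truncated normal | 37.7 | 4.8 | 30% | 0.650 | 35% |
| Truncated normal | 36.4 | 4.8 | 21% | 0.639 | 36% |
| Truncated normal | 43.1 | 7.0 | 64% | 0.596 | 40% |
| 30 + gamma | 36.0 | 5.0 | 17% | 0.631 | 37% |
| 30 + gamma | 40.0 | 8.0 | 39% | 0.600 | 40% |
| 30 + gamma | 42.0 | 8.0 | 51% | 0.552 | 45% |
| Truncated lognormal | 38.8 | 5.5 | 37% | 0.654 | 35% |
| Truncated lognormal | 41.2 | 7.3 | 50% | 0.611 | 39% |

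Across all 21 cases the loss is 33% to 45%, mostly 33% to 40%.

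**2. Comparison with an untruncated normal.** There R² = φ(c)²/[p(1−p)], where p is the share above the cut and c = z(1−p). The loss is 36% at p = 0.50, 40% at p = 0.35, 46% at p = 0.25 and 51% at p = 0.20. This shape fits the entry rule poorly. To have 20% above 40 and at most 2.5% below 30, the SD must be at most 10/(1.96 + 0.84) = 3.6; with 35% above 40, at most 10/(1.96 + 0.385) = 4.3.

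**3. Effect on the use as a main effect.** If BMI correlates r with change in ACT (assumed), the standard error of the treatment effect with the indicator, relative to continuous BMI, is √[(1 − r²R²)/(1 − r²)].
- r = 0.1, R² = 0.669: √(0.99331/0.99) = 1.002, or 0.2% wider.
- r = 0.3, R² = 0.552: √(0.95032/0.91) = 1.022, or 2.2% wider.
- r = 0.3, R² = 0.49 (untruncated normal, 20% above 40): √(0.9559/0.91) = 1.025, or 2.5% wider.

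**4. Effect on the interaction.** With SD 5 and all 38 observed, the difference between arms in slope per SD of BMI has a 95% half-width of 1.96 × 5 × √(4/38) = 3.2 ACT points when BMI is continuous. Estimating the same linear slope through the indicator divides this by √R²: 3.18/√0.669 = 3.9 to 3.18/√0.552 = 4.3.

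The contrast the plan would actually report is the treatment effect above 40 minus that below 40. Its half-width is 1.96 × 5 × √{4/[38p(1−p)]}: 6.7 points at p = 0.35 and 8.0 at p = 0.20, assuming arms balanced within BMI groups. All of these exceed the 2.8 points that the definitive trial targets.

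**The case against.** The strongest case against is that nothing of consequence changes. The primary comparison is unadjusted. Treatment-effect precision improves by about 2.5% at most under the assumed correlations. No form of the interaction can establish effect modification by BMI in 38 people, and the pilot's decision rests on the ACT confidence limit (section 3.3) and on feasibility outcomes (section 2.10), not on a BMI interaction. All of that stands, and it is why the point is minor.

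The covariate list is introduced as an open one, and section 3.1 also allows adjustment for baseline imbalance and alternative mean structures. Continuous BMI is therefore not ruled out. But the plan names only the indicator, and an open list does not supply the missing term.

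A step effect at 40 would make the cut harmless. That is true, but the plan offers no evidence of a step. A continuous term has its own weaknesses: it assumes approximate linearity, and a few very high BMI values can drive it in so small a sample. These call for a check on influence rather than a cut.

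Two stronger readings are tempting. A reader might infer that the cut discards 40% to 50% of the information. That needs an untruncated normal BMI with about 20% to 35% above 40, which sits badly with an entry limit of 30. A reader might also infer that the trial in effect analyses only about 19 to 25 of its 38 participants. That equivalence applies to the BMI coefficient alone; no participant drops out of any treatment comparison.

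**Conclusion.** The point holds as a minor one. BMI is named only as an indicator at 40 in the secondary main-effect and interaction models, without a reason, although baseline height and weight are measured. Under a roughly linear effect, the loss on the BMI term is about one third to 45%; under a true step at 40 it is zero. The range rests on assumed distributions limited to BMI above 30 and cannot be derived from the documents alone. It concerns the BMI coefficient and the treatment-by-BMI interaction only. The interaction remains exploratory and imprecise whichever form is used.

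**What to change.** In section 3.1, replace the indicator with baseline BMI as a continuous covariate, and say which pre-treatment visit supplies it. For the interaction, specify treatment by time by continuous BMI within the existing mixed model, and report the 24-week term with its confidence interval as exploratory. Add a check for influential BMI values and for gross departure from linearity. Keep the split at 40 for descriptive display.

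The cost is a sentence or two in the plan. No extra data, visits or participants are needed. What is accepted in return is a linearity assumption and some sensitivity to extreme BMI values.
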